2. Type 2 diabetes conversion: Yes/No

Other Variables of Interest among Subjects

1. Subject Demographics
 - a. Age (years)
 - b. Marital Status (single versus married)
 - c. Gender
 - d. Race/Ethnicity (African American, European American, or Hispanic, 2 parameters)
 - e. Specialty codes (categorized into office work, logistics, or combat specialties, 2 parameters)
 - f. Military Grade (Officer grades categorized into company, field or higher ranks; enlisted into E1 – E6 or E7 – E9).

Sample Size Estimation and Power Analysis: A priori power for H_01 was assessed using G*Power Version 3.0.10³. The results shown below indicate 214 subjects per group with 8 repeated measures for a total sample size of 3424 will achieve a power of approximately 0.99 to detect a small effect size of 0.10 at $\alpha = 0.0004$.

Input:	Effect size f	=	0.1
	β/α ratio	=	4
	Total sample size	=	3424
	Number of groups	=	2
	Repetitions	=	8
	Corr among rep measures	=	0.8
Output:	Noncentrality parameter λ	=	41.503030
	Critical F	=	12.389225
	Numerator df	=	1.000000
	Denominator df	=	3422
	α err prob	=	0.000437447
	β err prob	=	0.00174979
	Power (1- β err prob)	=	0.998250

[figure not shown]

Figure 1. rANOVA Power, $\beta = 0.002$, $\alpha = 0.0004$, 214 subjects per group

Post hoc analyses to evaluate differences within clinically significant time intervals will be tested with one-tailed t-tests for independent samples. The power analysis, using G*Power Version 3.0.10⁴, is shown below and shows 214 subjects per group will achieve a power of approximately 0.85 to detect a small effect size of 0.20. To lessen the probability of a false negative, a β/α ratio of 1 was employed.

t tests - Means: Difference between two independent means (two groups)

Analysis:	Compromise: Compute implied α & power		
Input:	Tail(s)	=	One
	Effect size d	=	0.2
	β/α ratio	=	1
	Sample size group 1	=	214
	Sample size group 2	=	214
Output:	Noncentrality parameter δ	=	2.068816
	Critical t	=	1.035015
	Df	=	426
	α err prob	=	0.150624
	β err prob	=	0.150624
	Power (1- β err prob)	=	0.849376

³ Faul F, Erdfelder E, Lang A-G, Buchner A. G*Power 3: A flexible statistical power analysis program for the social, behavioral, and biomedical sciences. *Behavior Research Methods*. 2007; 39 (2): 175-191.

⁴ Ibid.

[figure not shown]

Figure 2. *t*-test Power, $\beta = 0.15$, $\alpha = 0.15$, 214 subjects per group

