A priori power for H_02 was assessed using the method described by Glantz⁵ to calculate sample size for a two-sample log-rank test to detect differences in the time to event. Based on this design, it will require a minimum of 214 subjects per group to detect a difference between a 17.5% conversion in the placebo + lifestyle and an 11.5% conversion in the cinnulin + lifestyle group at $\alpha = 0.05$ (one-sided) and power of 0.80.

Power Analysis Log-Rank Test for Two Samples	
α	0.050
$Z_{.05(2)}$	1.64
$1-\beta$	0.80
$Z_{.80(\text{upper})}$	-0.842
$S_2(\infty)$	0.885
$\text{Ln}S_2(\infty)$	-0.122168
$S_1(\infty)$	0.825
$\text{Ln}S_1(\infty)$	-0.192372
ψ	0.6350597
d (primary endpoint events) =	124
n (sample size to achieve this number of events) =	428
Groups/Treatments	2
Subjects required per group/treatment	214

Steps of Analysis

Descriptive statistics: Sample means and standard errors of measurement of interval variables will be calculated, and frequency distributions of nominal variables will be calculated and graphed for the total sample and for the Cinnulin/Lifestyle Management groups. Homogeneity of the groups will be tested with a two-tailed *t*-test and two-tailed Fisher's exact test for interval and nominal variables respectively.

Hypothesis Testing

H_01 – This hypothesis will be tested by a mixed effects repeated measures analysis of variance (rANOVA).

H_02 – This hypothesis will be tested by developing Kaplan-Meier survival curves and survival functions compared with a log-rank test.

Post Hoc Tests: In the event H_01 is rejected, contrasts will be used to investigate effects and differences within clinically significant time intervals. In the event multiple univariate tests are used to investigate effects, the Bonferroni⁶ or Holm's method⁷ will be used to correct the level of significance for multiple comparisons.

Analysis Tools:

SAS Version 9.2 for Windows (SAS Institute, Cary, North Carolina)

R Version 2.13.1 (R Foundation for Statistical Computing)

Microsoft Excel (Microsoft Corporation, Seattle, Washington)

6.4 Number of Subjects:

Number of subjects recruited at WHASC	46
---------------------------------------	----

⁵ Glantz SA. *Primer of Biostatistics*. McGraw-Hill, 2002, 438-440.

⁶ Abdi H. Bonferroni and Šidák. Corrections for multiple comparisons. In N.J. Salkind (ed.). *Encyclopedia of Measurement and Statistics*. 2007; Thousand Oaks, CA: Sage.

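### The post hoc power of 0.85 and alpha of 0.15 are for one stand-alone, uncorrected t-test, not for the plan's procedure, which compares intervals only after H01 is rejected

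*Combined protocol and SAP*

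**What the plan says.** Section 6.3, under Sample Size Estimation and Power Analysis, sets out the interval comparisons: "Post hoc analyses to evaluate differences within clinically significant time intervals will be tested with one-tailed t-tests for independent samples". The power run is of the type "Compromise: Compute implied α & power", so alpha is an output and not a chosen level. The reason given is: "To lessen the probability of a false negative, a β/α ratio of 1 was employed". The inputs are d = 0.2, one tail and 214 per group. The outputs are critical t = 1.035015, "α err prob = 0.150624" and power 0.849376. The text concludes that the calculation "shows 214 subjects per group will achieve a power of approximately 0.85 to detect a small effect size of 0.20".

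Further on in section 6.3, Post Hoc Tests sets a condition: "In the event H_01 is rejected, contrasts will be used to investigate effects and differences within clinically significant time intervals". It adds that Bonferroni or Holm will be used if multiple univariate tests are run.

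H01 itself is tested by a mixed-effects repeated-measures ANOVA. Its power run, in section 6.3 and summarised in 6.2, uses f = 0.1, 2 groups, 8 repetitions, correlation 0.8 and a total sample size of 3424. It reports "Numerator df = 1.000000", denominator df 3422, alpha 0.000437447 and power 0.998250. No other significance level is given for H01. The one-sided 0.05 in sections 6.2 and 6.3 belongs to the log-rank test of H02.

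**The concern.** The power run and the Post Hoc Tests paragraph both concern differences within clinically significant time intervals, but they describe different procedures. The run treats the t-test as if every trial reached it. The paragraph makes it the second of two steps, so a difference can be declared only if H01 is rejected and the interval comparison is also significant. The chance of both cannot exceed the chance of either one.

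This matters because the post hoc step is the only place where the plan looks at specific intervals. Someone reading a trial with no declared interval difference could conclude from the printed figure that d = 0.20 had been looked for with 85% power, when the comparison might never have been made. Conversely, the printed 0.15 would suggest a 15% false-positive risk per comparison, which is not the rate of the gated rule when treatment has no effect at any visit.

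**Working it through.** **1. Reproduce the printed t-test figures.** Inputs from section 6.3: d = 0.20, 214 per group, one tail, β/α = 1.
- δ = 0.20 × √(214/2) = 2.0688, df = 426.
- Solving for the critical t at which β = α gives t = 1.0350, α = 0.1506 and power 0.8494.
- This matches the printed output exactly. The calculation contains neither a gate nor a multiplicity correction.

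**2. Reproduce the printed H01 figures.** For the between-group test, λ = N × f² × m / (1 + (m − 1)ρ), with f = 0.1, m = 8 and ρ = 0.8.
- N = 3424: λ = 3424 × 0.01 × 8 / 6.6 = 41.503. With β/α = 4, critical F = 12.389, α = 0.000437 and power = 0.99825. This also matches.
- But 3424 = 428 × 8, and m = 8 is already in the formula. Each subject is counted eight times and the repeated measures are then credited again.

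**3. H01 power with the design's 428 subjects.** λ = 428 × 0.01 × 8 / 6.6 = 5.188, df = 1 and 426.

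| H01 alpha | Source | H01 power |
|---|---|---|
| 0.000437 | printed | 0.105 |
| 0.05 two-sided | assumed, not in the documents | 0.623 |
| 0.077 | β/α = 4 kept, N = 428 | 0.693 |

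**4. Two-step rates.** Assumptions: d = 0.20 at every visit (the same as f = 0.10 for two equal groups), ρ = 0.8, the gate is the 1-df treatment effect, and one visit is then tested at t > 1.035 without correction. The correlation between the 8-visit mean and a single visit is √((1 + 7 × 0.8)/8) = √0.825 = 0.908. The gate statistic has mean √5.188 = 2.278 and the t statistic 2.069. The bivariate normal probability that both reject is:

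| Gate alpha | Two-step power | Rate if no effect at any visit |
|---|---|---|
| 0.000437 (printed) | 0.103 (simulation 0.107) | 0.0002 |
| 0.05 two-sided (assumed) | 0.620 (simulation 0.626) | 0.024 (simulation 0.024) |
| Printed for the t-test alone | 0.849 | 0.151 |

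The simulations used 8,000 trials each.

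**5. Sensitivity at the assumed 0.05 gate, 428 subjects.**
- ρ = 0.9: 0.58. ρ = 0.5: 0.74.
- Effects falling from 0.4 to 0.2, last visit tested: 0.84.
- Gate opened by treatment or treatment-by-time: 0.73 for an effect rising from 0.025 to 0.2, and 0.80 for an effect at the last visit only. The null rate is then 0.032.
- The same two late-effect patterns with a gate on the treatment effect alone: 0.25 and 0.05.
- Relaxing the gate to 0.10 at ρ = 0.8 gives 0.72.

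**6. Multiplicity.** Bonferroni on the stand-alone t-test, with no gate, gives 0.1506/2 = 0.0753 for two comparisons (power 0.74) and 0.1506/8 = 0.0188 for eight (power 0.49).

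**The case against.** The best defence takes the H01 block at face value. If the gate has power 0.998, two-step power is at least 0.8494 + 0.9983 − 1 = 0.848, and there is no shortfall. That arithmetic is right, but it depends on N = 3424, which the design does not have. Even then the printed alpha of 0.15 is not the rule's rate: with no effect at any visit, a step behind a gate at 0.000437 cannot give a false positive more often than 0.000437.

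A second defence is that the t-test block is correctly computed, is labelled as a t-test analysis and does not claim to be a joint power. That stands. The arithmetic is sound, and the fault is that it describes a different procedure from the one in Post Hoc Tests.

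A third is that H01 is worded broadly, between and among treatment groups, so a treatment-by-time test might also open the gate. That stands too, and it is why the gating test needs naming.

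A reader might go further and infer that the rule as written has power of at most 0.62 and a false-positive rate of about 0.02. The documents do not support this. They give no 0.05 level for H01, and 0.62 is not a bound: step 5 shows higher and lower values under other correlations, effect patterns and gates. Nor can the whole loss be charged to the gate alone, since it appears only once 3424 is replaced by 428.

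**Conclusion.** The point holds in this form: 0.85 and 0.15 are the rates of a single stand-alone, uncorrected one-tailed t-test, and they are not the operating characteristics of the gated, multiplicity-corrected procedure in Post Hoc Tests.

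With 428 subjects, ρ = 0.8, d = 0.20 at every visit and a gate on the treatment effect, the chance of declaring a difference at one visit before correction is about 0.10 at the only printed H01 alpha. It is about 0.62 if a two-sided 0.05 level is assumed. At that assumed level the alternatives examined mostly lie between 0.58 and 0.84, and lower for late effects behind a gate on the treatment effect alone. The null rates of about 0.0002 and 0.024 apply when there is no effect at any visit. If treatment acts at other visits, the gate opens more often and the rate at a null visit can rise, up to 0.15. Bonferroni or Holm cannot raise any of these probabilities.

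This concerns a secondary, post hoc step, but the figures are stated design properties and are cheap to correct.

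**What to change.** In the SAP (section 6.3, Sample Size Estimation and Power Analysis):
1. Label 0.85 and 0.15 as the power and alpha of one stand-alone, uncorrected t-test.
2. Redo the H01 power run with 428 subjects, and change the matching statement in section 6.2. Otherwise the new two-step figures would contradict the 0.998 left beside them.
3. State the significance level for H01 and which F-test opens the gate: treatment, treatment-by-time, or either.
4. Report two-step power and null rate for that rule, with the assumed correlation, effect pattern and number of corrected comparisons. If the printed alpha is kept and the treatment effect is the gate, these are about 0.10 and 0.0002 before correction. If two-sided 0.05 were chosen, they are about 0.62 and 0.024.

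The gate should not be deleted to recover the 0.85. That would remove a layer of error control in front of a one-tailed alpha of 0.15, and the stand-alone power would still fall to about 0.74 with two Bonferroni-corrected comparisons and 0.49 with eight.

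The cost is SAP and protocol wording plus a short recalculation, with no new data or participants. The downside is a less favourable stated power.

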6.2. Sample size estimation/power analysis:

A priori power for H₀₁ was assessed using G*Power Version 3.0.10¹. The results indicate 214 subjects per group with 8 repeated measures for a total sample size of 3424 will achieve a power of approximately 0.99 to detect a small effect size of 0.10 at α = 0.0004.

A priori power for H₀₂ was assessed using the method described by Glantz² to calculate sample size for a two-sample log-rank test to detect differences in the time to event. Based on this design, it will require a minimum of 214 subjects per group to detect a difference between a 17.5% conversion in the Placebo + lifestyle and an 11.5% conversion in the Cinnulin + lifestyle group at α = 0.05 (one-sided) and power of 0.80.

We are enrolling 557 subjects total, for an expected 428 completing the study. We estimate 129 subjects' will either withdraw consent or drop out of the study.

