⁷ Holm, S. 1979. A simple sequential rejective multiple test procedure. *Scand. J. Statistics*, 6: 65-70.

Number of subjects recruited at Nellis AFB	106
Number of subjects recruited at DGMC	76
Number of subjects recruited atEglin (actual)	53
Numerb of subject recruited at Offutt	2

TOTAL NUMBER OF SUBJECTS: 557 (nation-wide/study-wide): **428** (completing the study)

7. Duration of Study: Approximate duration of the study: 6 years

8. Intramural Funding/Local Support Services Required:

We received a grant for Intramural funding from the AFMSA/SG9S in the amount of approximately \$639,036.36. We received a second grant from the 59MDW/ST for approximately \$618,000 over 2 years. This is to support the salaries of four Medical Assistants, costs associated with Group Lifestyle Balance training, and site monitoring visits.

9. Extramural Funding/External Support Services Required:

Integrity Nutraceuticals, Inc. will provide Cinnulin PF and placebo to Geneva Research Foundation who will administer the grant. Collaborating Institution Support: This study will be sponsored by Integrity Nutraceuticals, Inc. The collaborative research will be executed in accordance with 15 USC 3710a through a Cooperative Research and Development Agreement, (pending approval) between the 99th MDG and Integrity Nutraceuticals, Inc. Integrity Nutraceuticals, Inc. shall provide the Air Force activity: 1 gram (2-500 mg capsules) Cinnulin PF tablets for approximately 279 subjects taking once a day for 1 year (\$280,370.00) and Placebo pills for approximately 279 subjects taking once a day for 1 year (\$1,870.00) to include shipping costs to the Air Force Activity. The estimated fair market value of the support is \$282,240.00.

10. Financial Conflict of Interest: No financial conflicts of interest exist.

11. Use of an Investigational New Drug, use of a Drug for a non-FDA approved purpose, use of an investigative device or use of a placebo:

This research uses an Investigational New Drug YES NO
This research uses a FDA approved drug for a non-FDA approved purpose YES
 NO
This research uses an Investigational Device YES NO
This research uses a placebo. YES
 NO

12. Medical Research Area for the Study: (Pick as many as appropriate)

 Analytical Chemistry	 Anatomy	 Anesthesiology	 Biochemistry

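### The H02 log-rank table treats the per-group number (428) as the total and halves it, so the planned size gives about 62 to 72 of the 124 required events and about 55 to 60% power, not 80%

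*Combined protocol and SAP*

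**What the plan says.** Section 6.3 (Sample Size Estimation and Power Analysis) sizes the log-rank test of H02 and concludes that "it will require a minimum of 214 subjects per group to detect a difference between a 17.5% conversion" on placebo and 11.5% on Cinnulin. The error rates are given as "α = 0.05 (one-sided) and power of 0.80", and section 6.2 carries the same statement.

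The log-rank table in 6.3 lists survival proportions of 0.825 and 0.885, ψ = 0.6350597, and then three linked rows:

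- "d (primary endpoint events"): 124
- "n (sample size to achieve this number of events"): 428
- required per group, after division by two groups: 214

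Enrolment is built on that result. Section 6.2 says: "We are enrolling 557 subjects total, for an expected 428 completing the study". The difference, 129, is the expected loss. Section 6.4 repeats the 557 and the 428.

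**The concern.** The table contradicts itself. If 428 subjects in total produced 124 events, 29.0% of them would convert (124/428). The plan's rates are 17.5% and 11.5%, which average 14.5% in two equal groups. The event row and the sample-size row are therefore a factor of two apart.

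Time to diagnosis of diabetes is the first goal in section 3.2, and the Technical Objective in 6.3 is prevention or delay of Type 2 diabetes. The table itself treats conversions as the primary events. If power is really 55 to 60%, the chance of missing the planned effect is 40 to 45%, about twice the 20% that the plan implies. A non-significant log-rank result read against a claimed 80% power would be taken as stronger evidence of no effect than it is.

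**Working it through.** **Inputs** (section 6.3 table and text; enrolment from 6.2): one-sided α = 0.05 (tabled z = 1.64), power 0.80 (tabled z = 0.842 in absolute value), S1 = 0.825 on placebo, S2 = 0.885 on Cinnulin, equal groups, 557 enrolled, 428 completing, 129 lost. The documents do not say over what period the 17.5% and 11.5% accrue. They are taken as end-of-study proportions, as the table's S(∞) notation implies.

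**Step 1: reproduce the plan's figures (Freedman log-rank formula).**

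- ψ = ln(0.885)/ln(0.825) = 0.1222/0.1924 = 0.635. This agrees.
- (1+ψ)/(1−ψ) = 1.63506/0.36494 = 4.480.
- d = (z_α + z_β)² × 4.480². With the tabled z values this is 123.7; with 1.645 and 0.842 it is 124.1. The table's 124 agrees.

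**Step 2: from events to subjects.** With n subjects *in each group*, expected events are n(1−S1) + n(1−S2) = n(2 − S1 − S2) = 0.29n. Setting this equal to d:

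- n per group = 124.1/0.29 = 428
- total = 2 × 428 = 856

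The match on 428 locates the slip: the number is right, but it is the size of one group, and the table halves it.

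**Step 3: other methods.** None gives 214 per group.

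| Method | Per group |
|---|---|
| Freedman, one-sided | 428 |
| Schoenfeld, one-sided (120 events) | 414 |
| Two proportions, one-sided | 425 (458 with continuity correction) |
| Log-rank, two-sided (153 to 158 events) | 528 to 545 |

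**Step 4: power at the planned size.** Freedman power = Φ(√events × (1−ψ)/(1+ψ) − 1.645), where (1−ψ)/(1+ψ) = 0.2232.

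- *428 completers:* 214 × 0.29 = 62.06 events; Φ(7.878 × 0.2232 − 1.645) = Φ(0.113) = 0.545. Schoenfeld gives 0.557, two proportions 0.547, and simulated log-rank tests 0.545 to 0.550.
- *Completers plus 129 dropouts, each censored at half follow-up (assumption):* 62.06 + 64.5 × [(1−√0.825) + (1−√0.885)] = 62.06 + 9.74 = 71.8 events; power 0.597. A simulation with dropout spread uniformly gives 71.6 events and 0.599.
- *Upper limit, all 557 followed in full:* 278.5 × 0.29 = 80.8 events; power 0.641 (simulated 0.643).
- *428 per group, as a check:* 124 events; power 0.800 (simulated 0.806).

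**Step 5: the effect for which 214 per group has 80% power.** Holding placebo at 17.5% and solving the Freedman equation for the Cinnulin rate gives 9.26%, or about 9.3% (ψ about 0.51, about 57 events). With the dropouts counted at half follow-up, the rate is about 9.8% (68 events).

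**The case against.** The arithmetic error is hard to dispute. The objections concern how its size is described.

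- *The 60% figure rests on an assumption.* The documents give no dropout timing. This stands, and the figure must be labelled as an assumption. The range free of it runs from 55% (completers only) to an unattainable ceiling of 64% (nobody lost). Neither end is close to 80%.
- *A completers-only count may not match the planned analysis.* The plan invokes intention-to-treat, so dropouts would contribute time at risk. That is fair, and is why the 72-event figure is shown beside the 62.
- *Sidedness is not settled.* The z value in the table carries a two-sided subscript, although 1.64 is the one-sided value, and the Hypothesis Testing step names no side. The one-sided reading is what the text states and is the more favourable: a two-sided test with 62 events has about 42% power.
- *No passage formally names a primary endpoint.* The stated Purpose is lowering blood glucose, and the outcome list in 6.1 omits conversion. This tempers the argument about importance. But conversion is the first goal, the Technical Objective and the table's own label, and a stated power should be correct in any case.
- *The planned size may not be the actual size.* The site counts in 6.4 are 46 + 106 + 76 + 53 + 2 = 283, not 557, and only one is marked as actual. Their status is unclear. This affects the replacement figures, not the finding that the table is wrong.

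**Conclusion.** The concern holds. The table takes a per-group requirement for a total, and the power of 0.80 stated in 6.2 and 6.3 does not follow from the plan's own rates. For 17.5% against 11.5% at one-sided 0.05, the planned 428 completers give 62 events and about 55% power. This needs only the documents' figures and the reading of the two rates as end-of-study proportions. About 72 events and 60% power depend on the half-follow-up assumption for dropouts. Full follow-up of all 557 would reach 81 events and 64%, so no reading recovers 80%.

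The error does not reach the H01 power calculation, which is separate. That calculation is not assessed here.

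**What to change.** 1. In the 6.3 table, keep d = 124 and correct the rows below it to 856 in total and 428 per group.
2. If enrolment is not changed, replace the power statement in both 6.2 and 6.3. For 17.5% against 11.5% at one-sided 0.05, the planned size gives about 62 events and 55% power with 428 completers, and about 72 events and 60% power if the 129 dropouts are counted as censored at half follow-up. Mark the second figure as resting on that assumption.
3. Add that, with placebo conversion held at 17.5%, 214 per group has 80% power only if conversion on Cinnulin is about 9.3% or lower.
4. Once the number actually randomised is confirmed, recompute the statement for the same planned effect, 17.5% against 11.5%.

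The cost is a table correction and wording in two sections. No patients are added, and no hypothesis or test changes. The stated power becomes less favourable. For comparison, keeping 80% power for the planned effect would take 856 completers, or 856 × 557/428 = 1,114 enrolled at the plan's own dropout rate.
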